See Table D1 for the procedures and assessment to be performed for the Month 1 visit of the study. Subject visits should be completed as close to the scheduled visit dates as possible. There will be a +/- window of 2 weeks for the month 1 study visit.

D.15.5 Month 3 and Month 6 Visit

See Table D1 for the procedures and assessment to be performed for month 3 and 6 visit of the study. Subject visit should be completed as close to the scheduled visit dates as possible. There will be a +/- window of 30 days for the month 3 and 6 study visit.

D.15.6 Month 12 Visit

See Table D1 for the procedures and assessments to be performed for Month 12 visit. This visit will be conducted via a phone interview with the subject. A phone script will be provided to the study personnel to use when interviewing the subject. There will be a +/- window of 2 weeks for this visit.

11. Reference List

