8.2.4 Subject Stopping Guidelines

This guideline is to be used to indicate boundaries requiring discussion by the Data and Safety Monitoring Board (DSMB) and is designed to assist the independent DSMB in overseeing the study. The DSMB may also request additional interim analyses and develop other criteria including provision for monitoring of potential late effects to determine when to intervene in the enrollment or treatment of subjects in the study. The first more conservative stopping guideline is to monitor subjects for unexpected SAEs where there is a reasonable possibility that the study product or administration procedure caused the event within 30 days of administration including subject death, grade 3 myocardial infarction, or grade 3 hemodynamically unstable ventricular tachycardia. Study accrual and further treatment of subjects will be put on hold if any subjects experience one of these events. The DSMB will be notified within 24 hours of the occurrence of these events and will be convened within 3 business days to review the event and study.

The following are subject stopping guidelines:

1. Any subject who develops persistent (that is, still existing more than 3 hours after the end of IP infusion) cardiorespiratory signs or symptoms (for example, shortness of breath, tachypnea, tachycardia, hypotension, or palpitations) will continue with all scheduled follow-up if such follow-up is considered safe in the opinion of the Investigator. A subject may still be able to receive additional infusions, based on the investigator's judgement.
2. Any subject whose infusion is stopped due to cardiorespiratory distress will not receive further IP infusions until it is considered safe in the opinion of the Investigator, but subjects will continue with all scheduled follow-up if such follow-up is considered safe. A subject may still be able to receive additional infusions, based on the investigator's judgement.
3. The proportion of subjects experiencing TE-SAE as defined in Section 2.2.1 will be monitored within 30 days of infusion. This guideline is designed to assist the independent DSMB in overseeing the study and indicate boundaries needing discussion by the DSMB. The DSMB may also request additional interim analyses and develop other criteria including provision for monitoring of potential late effects to determine when to intervene in the enrollment or treatment of subjects in the study.

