See Table A1 for the procedures and assessments to be performed for Month 12 visit. This visit will be conducted via a phone interview with the subject. A phone script will be provided to the study personnel to use when interviewing the subject. There will be a +/- window of 2 weeks for this visit.

A.16 Statistical Considerations

All subjects will be offered the re-infusion and formal statistical considerations regarding sample size and power are not provided. Based on prior studies, a second infusion of stem cells are safe but strict safety monitoring will be employed to continue the safety assessment of allogeneic infusion of MSCs. Detailed analyses will be described in the separate statistical analysis plan.

A.17 Safety Monitoring of 30-Day Rate of TE-SAEs

Monitoring of the rate of TE-SAEs by 30-days post-second infusion among subjects who received the infusion of allogeneic MSCs will be employed to assist the DSMB in prospective monitoring of this study. The guideline is to be used to indicate boundaries requiring discussion by the DSMB and is designed to assist the independent DSMB in overseeing the study. The DSMB may also request additional interim analyses and develop other criteria including provision for monitoring of potential late effects to determine when to intervene in the enrollment or treatment of subjects in the study. Monitoring of key safety endpoints will be conducted. If rates significantly exceed the pre-set threshold, then the DSMB will be notified.

A Bayesian motivated safety stopping guideline for monitoring the 30-day TE-SAE rate will be used for this trial. The expected underlying rate of TE-SAE at 30 days post-second infusion is assumed to be 13.3% based on the assumption that 2 out of 15 subjects experience a TE-SAE. It would then be assumed that a rate of greater than 40.0% is unacceptable.

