A Beta distribution can be used as the prior distribution of θ ; where θ is the proportion of subjects who experience an TE-SAE by 30-days post-second infusion. The stopping rule is based on the beta-binomial methodology and assumes a prior expected failure rate. This leads to prior Beta parameters where $a=0.8$ and $b=5.2$. The Beta distribution will have a prior mean of 0.13 and a prior probability of <0.05 of exceeding 0.40. The guideline is derived such that there is strong evidence (posterior probability >0.95) that the probability of the event is greater than 40%, the trial will be stopped. The resulting boundaries tabulated in Table A2 were rounded to be conservative with the stopping guideline and is considered after 5 subjects are enrolled on the study.

TABLE A2

Bayesian Stopping Guideline for Event Rate of 13% *

# Events	# Subjects in Study
3	5
4	6-9
5	10-14
6	15

* The stopping guidelines serve as a trigger for consultation with the DSMB for additional review, and are not formal “stopping rules” that would mandate automatic closure of study enrollment.

A simulation study was conducted to evaluate the operating characteristics of this stopping rule. Data were generated from the binomial distribution with varying probabilities of failure (θ) and assuming a sample size of 15 subjects. Table A3 shows the probability of stopping the trial early and the average sample size (N), conditional on stopping early, at which the boundary is crossed for each value of θ . The unconditional average sample size of the trials for each value of θ is displayed.

Table A3

Operating Characteristics for Bayesian Motivated Stopping Guideline

Mean of Prior Distribution	θ	Probability of stopping	Conditional Average Sample Size (N)	Unconditional Average Sample Size of Trials (N)
0.13	0.13	0.05	8.4	14.7
	0.18	0.12	8.8	14.2
	0.23	0.25	8.9	13.5
	0.28	0.40	8.8	12.5
	0.33	0.56	8.5	11.4
	0.40	0.75	8.0	9.8

Although the motivation for the boundary is Bayesian, the operating characteristics can be evaluated from a frequentist perspective of Type I error and power. The stopping rule for a 13% event rate has a 5% chance (“Type I error”) of suggesting early termination when the true rate is 0.13, and a 75% chance (“power”) when the true rate is 0.40.

Limitations

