A major limitation to the second infusion approach is the small sample size. While it is assumed that all 15 subjects will be eligible for a second infusion, there is a chance that subjects will not want to undergo a second infusion and thus would further limit the amount of information received. However, the second infusion strategy is being implemented to obtain information on the safety of a second infusion of allogeneic MSCs to help guide future studies.

Addendum B: Penicillin/streptomycin free cell safety study

B.1 Rationale and Description for penicillin/streptomycin free cell safety study

This addendum to the protocol is designed to gain additional safety of penicillin/streptomycin free intravenous infusion of allo-hMSCs in subjects with aging frailty. Up to twenty subjects will be recruited to participate in a single dose of allogeneic MSCs in this follow-on phase. All study specific processes and procedures included in the protocol apply in this addendum unless otherwise noted. This population will not be included in the main phase of the trial, which included 15 pilot and 30 randomized subjects. Additionally, subjects receiving a dose in the penicillin/streptomycin free study are eligible to receive up to three (3) additional infusions.

B.2 STUDY OBJECTIVES AND ENDPOINTS

B.2.1 Study Objectives

B.2.1.1 Primary Objective

1. Demonstrate the safety and tolerability of penicillin/streptomycin free intravenous infusion of allo-hMSCs in subjects with aging frailty.

B.2.1.2 Secondary Objectives

6. To explore treatment efficacy (decrease in frailty, frequency of acute exacerbations, change in symptom related quality of life, improved cardiovascular status, decrease in inflammatory biomarkers, endothelial function and 1 year survival).

B.2.2 Study Endpoints

B.2.2.1 Primary Endpoints (Safety)

1. Safety (Primary): Incidence (at one month post second infusion) of any treatment-emergent serious adverse events (TE-SAEs), defined as the composite of: death, non-fatal pulmonary embolism, stroke, hospitalization for worsening dyspnea and clinically significant laboratory test abnormalities, determined per the Investigator's judgment.

- Laboratory tests included in the primary endpoint include the following:

- Serum chemistry: chloride, sodium, Carbon Dioxide, BUN, creatinine, glucose, calcium, AST/SGOT, ALT/SGPT, total bilirubin (fractionate if total >1.5 times normal), alkaline phosphatase, albumin,

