The Month 12 visit will be waived if screening visits for subsequent infusions take place prior to this visit.

B.15 Statistical Considerations

All subjects will be offered the penicillin/streptomycin free hMSCs and formal statistical considerations regarding sample size and power are not provided. Based on prior studies, stem cells are safe but strict safety monitoring will be employed to continue the safety assessment of penicillin/streptomycin free allogeneic infusion of MSCs. No detailed analyses will be described in the statistical analysis plan.

B.16 Safety Monitoring of 30-Day Rate of TE-SAEs

Monitoring of the rate of TE-SAEs by 30-days post infusion among subjects who received the infusion of penicillin/streptomycin free allogeneic MSCs will be employed to assist the DSMB in prospective monitoring of this study. The guideline is to be used to indicate boundaries requiring discussion by the DSMB and is designed to assist the independent DSMB in overseeing the study. The DSMB may also request additional interim analyses and develop other criteria including provision for monitoring of potential late effects to determine when to intervene in the enrollment or treatment of subjects in the study. Monitoring of key safety endpoints will be conducted. If rates significantly exceed the pre-set threshold, then the DSMB will be notified.

A Bayesian motivated safety stopping guideline for monitoring the 30-day TE-SAE rate will be used for this trial. The expected underlying rate of TE-SAE at 30 days post-infusion is assumed to be 10% based on the assumption that 2 out of 20 subjects experience a TE-SAE. It would then be assumed that a rate of greater than 40.0% is unacceptable.

A Beta distribution can be used as the prior distribution of θ ; where θ is the proportion of subjects who experience an TE-SAE by 30-days post infusion. The stopping rule is based on the beta-binomial methodology and assumes a prior expected failure rate. This leads to prior Beta parameters where $a=0.8$ and $b=5.2$. The Beta distribution will have a prior mean of 0.13 and a prior probability of <0.05 of exceeding 0.40. The guideline is derived such that there is strong evidence (posterior probability >0.95) that the probability of the event is greater than 40%, the trial will be stopped. The resulting boundaries tabulated in table B2 were rounded to be conservative with the stopping guideline and is considered after 5 subjects are enrolled on the study.

TABLE B2

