Bayesian Stopping Guideline for Event Rate of 10% *

# Events	# Subjects in Study
3	5
4	6-9
5	10-14
6	15

* The stopping guidelines serve as a trigger for consultation with the DSMB for additional review, and are not formal “stopping rules” that would mandate automatic closure of study enrollment.

A simulation study was conducted to evaluate the operating characteristics of this stopping rule. Data were generated from the binomial distribution with varying probabilities of failure (θ) and assuming a sample size of 15 subjects. Table B3 shows the probability of stopping the trial early and the average sample size (N), conditional on stopping early, at which the boundary is crossed for each value of θ . The unconditional average sample size of the trials for each value of θ is displayed.

Table B3
Operating Characteristics for Bayesian Motivated Stopping Guideline

Mean of Prior Distribution	θ	Probability of stopping	Conditional Average Sample Size (N)	Unconditional Average Sample Size of Trials (N)
0.13	0.13	0.05	8.4	14.7
	0.18	0.12	8.8	14.2
	0.23	0.25	8.9	13.5
	0.28	0.40	8.8	12.5
	0.33	0.56	8.5	11.4
	0.40	0.75	8.0	9.8

Although the motivation for the boundary is Bayesian, the operating characteristics can be evaluated from a frequentist perspective of Type I error and power. The stopping rule for a 13% event rate has a 5% chance (“Type I error”) of suggesting early termination when the true rate is 0.13, and a 75% chance (“power”) when the true rate is 0.40.

Limitations

A major limitation to this approach is the small sample size. However, the penicillin-streptomycin free infusion strategy is being implemented to obtain information on the safety of a penicillin/streptomycin free allogeneic MSCs to help guide future studies.

Addendum C: Pilot and Penicillin/Streptomycin Free Subjects Optional Follow-on Phase

C.1 Rationale and Description of additional infusions for subjects who have received one or two infusions in the phase I open-label phases of this protocol.

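### The 40% posterior criterion worded in A.17 and B.16 does not produce Tables A2/B2; the tables correspond to a threshold of 2/15 (13.3%)

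*Combined protocol and SAP*

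**What the plan says.** A.17 sets the expected 30-day TE-SAE rate after the second infusion, which "is assumed to be 13.3% based on the assumption that 2 out of 15 subjects experience a TE-SAE", and calls a rate above 40% unacceptable. It gives a Beta(0.8, 5.2) prior, with mean 0.13 and less than 0.05 probability above 0.40. The decision criterion is "strong evidence (posterior probability >0.95) that the probability of the event is greater than 40%, the trial will be stopped". Table A2 is then given as what this criterion produces, after some conservative rounding and with the first look at 5 subjects. Table A3 reports the simulated chance of stopping within 15 subjects: 5% at a true rate of 0.13, rising to 75% at 0.40. The footnote to Table A2 softens the stop: "The stopping guidelines serve as a trigger for consultation with the DSMB for additional review".

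B.16 repeats the criterion, the prior, the boundaries and the operating characteristics. Yet its expected rate "is assumed to be 10% based on the assumption that 2 out of 20 subjects experience a TE-SAE", Table B2 is titled for a 10% event rate, and B.1 says "Up to twenty subjects will be recruited to participate in a single dose of allogeneic MSCs". Table B2 and its simulation end at 15.

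**The concern.** The prior mean is about 13%, yet three events in five subjects are said to make it more than 95% certain that the rate is above 40%. The observed proportion at that boundary is 60%, and at the last boundary (6/15) it is exactly 40%. With the prior pulling downwards, 6/15 cannot put 95% of the posterior above 40%.

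If criterion and table are different rules, two things are at stake. A DSMB told that the boundary was crossed would read it as strong evidence of a rate the plan calls unacceptable, when the data support a much weaker statement. And anyone who implements the sentence instead of the table gets a guideline that almost never alerts the DSMB. These are the only rate-based safety boundaries that the document gives in numbers.

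**Working it through.** **Inputs** (A.17, repeated in B.16): prior a = 0.8, b = 5.2; cut-off 0.95; worded threshold 0.40; first look at n = 5; maximum n = 15; expected rate 2/15 in A.17.

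**Formula.** After x events in n subjects the posterior is Beta(0.8 + x, 5.2 + n − x). The boundary at n is the smallest x with P(θ > t | x, n) > 0.95.

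**Prior check.** Mean = 0.8/(0.8 + 5.2) = 0.133, and P(θ > 0.40) = 0.049. Both agree with the text, so the inputs are read correctly.

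**Boundaries under candidate thresholds t**

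| n | Tables A2/B2 | t = 0.40 (as worded) | t = 2/15 | t = 0.13 |
|---|---|---|---|---|
| 5 | 3 | none | 3 | 3 |
| 6-7 | 4 | none | 4 | 4 |
| 8 | 4 | 8 | 4 | 4 |
| 9 | 4 | 9 | 4 | 4 |
| 10 | 5 | 9 | 5 | 4 |
| 11-12 | 5 | 10 | 5 | 5 |
| 13-14 | 5 | 11 | 5 | 5 |
| 15 | 6 | 12 | 6 | 5 |

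Examples for t = 0.40: 7/7 gives 0.928 (not enough), 8/8 gives 0.959, 11/15 gives 0.933 (not enough), 12/15 gives 0.974.

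**Posterior at the printed boundaries.** P(θ > 0.40) is 0.334 at 3/5, 0.484 at 4/6, 0.140 at 5/14 and 0.221 at 6/15; over all eleven sample sizes it runs from 0.14 to 0.48. P(θ > 2/15) runs from 0.954 to 0.987, and with one event fewer it is at most 0.949. So 2/15 with cut-off 0.95 fits exactly. On a grid of 0.0001, thresholds from 0.1324 to 0.1366 also fit. The rounded 0.13 fails at n = 10 and n = 15. With t = 0.40, no cut-off from 0.01 to 0.998 gives the table.

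**Probability of crossing by n = 15** (exact recursion, one look after each subject from n = 5)

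| True rate | Tables A3/B3 | Printed boundary | Worded 40% rule |
|---|---|---|---|
| 0.13 | 0.05 | 0.044 | about 2 × 10⁻⁷ |
| 0.18 | 0.12 | 0.123 | < 0.0001 |
| 0.23 | 0.25 | 0.245 | < 0.0001 |
| 0.28 | 0.40 | 0.397 | 0.0002 |
| 0.33 | 0.56 | 0.556 | 0.0010 |
| 0.40 | 0.75 | 0.750 | 0.0055 |

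The unconditional mean sample sizes also match Table A3: 14.7, 14.2, 13.5, 12.5, 11.4 and 9.8. The small gap at 0.13 could be simulation error or the use of 2/15 (exact 0.048); nothing rests on it. The worded rule reaches only 3.5% at a true rate of 0.50 and 14.0% at 0.60.

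**Addendum B.** With the same prior, t = 0.10 gives 3 events at n = 5-8, 4 at 9-14 and 5 at 15-20, so the 10% in the title of Table B2 does not generate it either. As printed, with no boundary after 15, it is crossed with probability 1.9% at a true rate of 0.10. Extending the 2/15 rule to 20 subjects gives 6 events at n = 15-20, with crossing probability 2.4% at 0.10 and 89% at 0.40.

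**The case against.** The best defence is that the printed table is what the DSMB uses. It agrees with its operating characteristics, and nobody has to derive a boundary from the sentence. The opening of A.17, the table footnotes, 8.2.4 and 9.3 all make the boundaries a prompt for DSMB discussion, so the stop wording misleads few readers. Section 8.2.4 also has a separate hold: "Study accrual and further treatment of subjects will be put on hold if any subjects experience one of these events". C.1 reports that 12 subjects had already received two doses and 20 the antibiotic-free dose, and Addendum C, still offering infusions, has no such table.

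Most of this stands and limits the consequence: a reader who follows the table loses no protection. It does not rescue the sentence. The 8.2.4 hold covers unexpected SAEs within 30 days that are possibly due to the product or procedure (death, grade 3 myocardial infarction and unstable ventricular tachycardia are named); it sets no TE-SAE rate. Conservative rounding cannot turn 12/15 into 6/15, or an unattainable boundary into 3/5. And the meaning of crossing, or not crossing, still has to be reported correctly after dosing is complete.

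It is also fair that B's 10% rate and 20 subjects are a partly separate matter. They belong here because correcting the threshold in B.16 forces a choice about which rate Table B2 represents.

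**Conclusion.** The concern holds. Under the stated prior, the worded criterion and Tables A2/B2 are different rules: 12 events against 6 at n = 15, and a 0.55% against a 75% chance of alerting the DSMB at a true rate of 40%. Tables A2 and A3 agree with each other, so the error lies in the sentence.

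That the intended threshold was 2/15 is an inference: it is the stated expected rate and fits all eleven boundaries, but neither addendum names it as the posterior threshold. That the 40% wording is wrong does not depend on this inference. Correctly read, a crossing is strong evidence (posterior 0.954 to 0.987) that the rate exceeds 13.3%. It is not strong evidence that the rate exceeds 40%.

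This should be fixed. With consultation as the only consequence and dosing reported in both cohorts, the effect is mainly on interpretation and reporting.

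**What to change.** **A.17.** State the criterion as posterior probability above 0.95 that the rate exceeds the expected 13.3% (2/15). Keep 40% only as the unacceptable rate at which 75% detection is quoted. Say that a crossing leads to DSMB consultation, in line with the footnote. Leave Tables A2 and A3 as they are. Cost: one sentence.

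**B.16.** Make the same correction to the threshold and the stop wording. Then, preferably, say that Table B2 uses a 13.3% threshold, correct its 10% title, extend it with 6 events at n = 15-20, and recompute Table B3 for 20 subjects (2.4% at 0.10, 89% at 0.40).

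An optional alternative is to re-derive B for its stated 10% rate. With the same prior, the boundary is 3 events at n = 5-8, 4 at 9-14 and 5 at 15-20 (7.7% at 0.10, 96% at 0.40). With an assumed Beta(0.6, 5.4) prior of mean 0.10, it is 3 at 5-7, 4 at 8-13, 5 at 14-19 and 6 at 20 (6.1% and 94%). The price is more consultations at an acceptable rate.

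Neither route changes data collection. The cost in meaning is that a crossing carries a weaker, but correct, claim.
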